## 10. STUDY ASSESSMENTS

The procedures and assessments that will be conducted during this study are described in this section and summarized in the Schedule of Assessments ([Table 24](#)). Detailed instructions regarding all laboratory procedures, including collection and handling of samples, will be included in the study Laboratory Manual provided by the Sponsor.

The schedule for collection of blood samples for analysis of CCI [REDACTED] is presented in [Table 25](#). The schedule for collection of samples for CCI [REDACTED] analyses is presented in [Table 26](#). The schedule for collection of samples for CCI [REDACTED] analyses is presented in [Table 27](#).

Written informed consent must be granted by each patient prior to the initiation of any study procedure or assessment, including assessment of histology.

Planned timepoints for all safety assessments are provide in the Schedule of Assessments ([Table 24](#)). Unscheduled safety measurements may be obtained at any time during the study to assess any perceived safety issues.

**Table 24. Schedule of Assessments**

ACTIVITY	Screening	Cycle 1 Day in Cycle 21-day cycle		Cycle 2 – Cycle 6 Day in Cycle ( $\pm$ 1 day) 21-day cycles		Subsequent Cycles Day in Cycle ( $\pm$ 3 days) 28-day cycles		Safety Follow-Up Visit ff	Long-Term Follow- Up
		Day -28 to -1	1	8	1	8	1		
Informed Consent	X								
Demographics	X								
Inclusion and exclusion criteria	X								
Medical history	X								
Cancer history	X								
Physical exam, vital signs a	X	X		X		X		X	
Confirmation of histology in an archival or fresh tissue specimen b		X							
Brief physical exam, vital signs c			X		X		X		
LVEF d	X			X w		X w		X	
ECOG PS	X	X		X		X		X	
Serum chemistry e	X	X t	X t	X t	X t	X t	X t	X	
Hematology f	X	X t	X t	X t	X t	X t	X t	X	
Coagulation g	X	X t							
ECG h	X	X t		X u		X v		X	
Pregnancy test i	X	X		X		X		X	
Radiologic assessment of disease status j	X	X					X		X
PRO QoL assessment k		X		X		X		X	
Administer doxorubicin with prophylaxis l		X		X					
Cardiotoxicity prophylaxis m				X m					
Administer TTI-621 with prophylaxis n		X	X	X	X	X	X		
Adverse events				Ongoing					
Concomitant medications and procedures				Ongoing					

ACTIVITY	Screening	Cycle 1 Day in Cycle 21-day cycle		Cycle 2 – Cycle 6 Day in Cycle ( $\pm$ 1 day) 21-day cycles		Subsequent Cycles Day in Cycle ( $\pm$ 3 days) 28-day cycles		Safety Follow-Up Visit **	Long-Term Follow- Up
		Day -28 to -1	1	8	1	8	1		
	CC1								
Survival, initiation of new anti-cancer therapy a									x

- a Complete physical examination by body system, including vital signs (temperature, blood pressure, pulse rate, respiratory rate, weight, pulse oximetry); height collected during screening only
- b Expansion phase only and patients with a diagnosis of leiomyosarcoma; to be performed in a central laboratory; patient may be enrolled based on a current or most recent pathology report that provides sufficient detail to support derivation of the histologic interpretation but a pre-treatment tissue specimen must be made available for confirmation during screening or within the first cycle of treatment
- c Symptom-directed physical examination, with vital signs limited to temperature, blood pressure, pulse rate, respiratory rate
- d Assessed by transthoracic echocardiogram or MUGA
- e Glucose, sodium, potassium, calcium, chloride, phosphate, bicarbonate, blood urea nitrogen or urea, creatinine, total protein, albumin, alkaline phosphatase, aspartate aminotransferase (AST), alanine aminotransferase (ALT), total bilirubin, indirect bilirubin, uric acid, calcium, magnesium, lactate dehydrogenase (LDH)
- f Hemoglobin, hematocrit, platelets, white blood cells (WBC), neutrophils, lymphocytes, eosinophils, basophils, monocytes, WBC with automated 5-part differential, RBC, absolute reticulocytes, reticulocytes %, MCH, MCV, RDW
- g International normalized ratio (INR)/prothrombin time (PT), partial thromboplastin time (PTT). To be repeated more frequently if clinically-indicated (e.g., INR/PT for patients on anti-coagulants)
- h 12-lead ECG, average of triplicate assessments obtained with patient in supine position and within 10 minutes total time; to be performed prior to Cycle 1, Cycle 3, Cycle 4 and Cycle 6; prior to every third cycle beginning with Cycle 7; and at the Safety Follow-Up Visit.
- i Pregnancy tests will be performed in WOCBP. A serum pregnancy test is required at screening. Following screening, pregnancy tests may be urine or serum tests, and must have a sensitivity of at least 25 mIU/mL. At baseline and when scheduled at treatment visits, must be performed prior to treatment.
- j Assessed objectively by CT, MRI or PET/CT; the method used at baseline should be used for the duration of patient participation. Performed every  $6 \pm 1$  week for the first 18 weeks (during combination treatment), every  $8 \pm 1$  week until Week 50 or patient has been on study for one year, and every  $12 \pm 2$  weeks thereafter. CR or PR should be confirmed by repeat assessment at least four weeks after initial observation; treatment can continue during the interval between initial observation and confirmation. In the event that a patient is removed from the study in the absence of radiologic disease progression, a radiologic disease assessment should be performed at the Safety Follow-Up Visit if not performed within the previous four weeks and disease status should be assessed during Long-Term Follow-Up until radiologic demonstration of progression or initiation of new anti-cancer therapy, whichever occurs first
- k Patient-reported health-related quality of life will be assessed with the EORTC QLQ-C30 tool on Day 1 of every cycle and at the Safety Follow-Up visit prior to initiation of study treatment or other study activities

- i Doxorubicin should be administered through a free-flowing catheter at 75 mg/m^2 by intravenous infusion in less than 60 minutes. Prophylaxis against emesis and for prevention of febrile neutropenia should be administered as described in [Section 5.2.1.1](#); additional prophylaxis in accordance with institutional guidelines is acceptable
- m Cardioprotective administration of [dexrazoxane](#) should be initiated no later than initiation of Cycle 5 unless earlier initiation is medically advised or standard of care at a particular institution
- n Prophylaxis as described in [Section 5.2.1.2](#) will be initiated at least 30-60 minutes prior to initiation of TTI-621 infusion. TTI-621 is administered intravenously over 2 hours. At the Investigator's discretion and in the absence of infusion-related reaction in prior cycles, duration of infusion may be reduced to 60 minutes beginning with Cycle 2. Patients should be observed for one hour after infusion with vital signs assessment in 30-minutes for signs of infusion-related reaction in Cycle 1; the observation period may be reduced at the Investigator's discretion in patients who tolerate the infusion well and do not experience infusion-related reaction.
- o Detailed sample collection schedule provided in [Table 25](#)
- p Detailed sample collection schedule provided in [Table 27](#)
- q Detailed sample collection schedule provided in [Table 26](#)
- r Detailed sample collection schedule provided in [Table 27](#)
- s Assessed every 12 ± 2 weeks; telephone contact is acceptable
- t Does not need to be performed if previous assessment was within 72 previous hours
- u Prior to initiation of Cycle 3, Cycle 4 and Cycle 6; does not need to be performed if previous assessment was within seven days
- v Prior to initiation of every third cycle (Cycle 7, Cycle 10, Cycle 13, etc.); does not need to be performed if previous assessment was within seven days
- w Prior to initiation of Cycles 5 and 8; does not need to be performed if previous assessment was previous four weeks
- x Participants with an unresolved AE considered by the Investigator as possibly related to or associated with [REDACTED] will be asked to return for [REDACTED] blood sampling at approximately 3-month intervals (if feasible given the underlying disease) until the last follow-up of the AE up to a maximum of 12 months. [REDACTED]
- y Cycles 2, 3, 4, 5 only
- z Cycle 2 and Cycle 3 only
- aa Every second cycle (Cycle 7, Cycle 9, Cycle 11, etc.)
- bb Cycle 7 only
- CCI**  
[REDACTED]
- dd May be collected anytime within seven days prior to and 14 days after Cycle 3 Day 1; other times may be acceptable after consultation with Sponsor
- CCI**  
[REDACTED]
- ff To be performed 30 + five days after last administration of study treatment or before initiation of subsequent anti-cancer therapy, whichever occurs first

Table 25. Sample Collection Schedule for Analysis of CCI

Cycle	CCI
Day of Cycle	
Timepoint(s)	

CCI

Table 26. Sample Collection Schedule for Analysis of CCI

Cycle	CCI
Day of Cycle	
Timepoint	

CCI

Table 27. Sample Collection Schedule for Analysis of [REDACTED]

Screening	CCI	CCI
CCI		

**11. SCHEDULE OF PROCEDURES AND ASSESSMENTS**

The following procedures and assessments will be performed at the indicated timepoints.

***Screening Visit (Day -28 to -1)***

- Informed consent
- Demographics
- Inclusion and exclusion criteria
- Medical history
- Cancer history
- Complete physical examination
- Vital signs (temperature, blood pressure, pulse rate, respiratory rate, weight, pulse oximetry), height
- **CCI** [REDACTED]
- LVEF by transthoracic echocardiogram or MUGA
- ECOG PS
- Serum chemistry
- Hematology
- Coagulation
- 12-lead ECG
- Urine or serum pregnancy test (female patients of childbearing potential only)
- Radiologic assessment of disease status using CT, MRI or PET/CT; the method used at baseline should be used for the duration of patient participation
- Blood collection for **CCI** [REDACTED]

***Cycle 1 Day 1***

- Patient-reported quality-of-life assessment
- Complete physical examination
- Vital signs (temperature, blood pressure, pulse rate, respiratory rate, weight, pulse oximetry)
- ECOG PS
- Serum chemistry (unless previous assessment was performed within previous 72 hours)
- Hematology (unless previous assessment was performed within previous 72 hours)
- Coagulation (unless previous assessment was performed within previous 72 hours)
- 12-lead ECG (unless previous assessment was performed within previous 72 hours)
- Urine or serum pregnancy test (female patients of childbearing potential only; must be performed prior to treatment) Administer doxorubicin with prophylaxis
- Administer TTI-621 with prophylaxis
- 60-minute observation period after TTI-621 infusion; vital signs assessed in 30-minute intervals
- Adverse events
- Concomitant medications and procedures
- Blood collection for **CCI** [REDACTED]
- Blood collection for [REDACTED]
- Blood collection for [REDACTED]

**Cycle 1 Day 8**

- Brief physical examination
- Vital signs (temperature, blood pressure, pulse rate, respiratory rate)
- Serum chemistry (unless previous assessment was performed within previous 72 hours)
- Hematology (unless previous assessment was performed within previous 72 hours)
- Administer TTI-621 with prophylaxis
- 60-minute observation period after TTI-621 infusion; vital signs assessed in 30-minute intervals
- Adverse events
- Concomitant medications and procedures
- Blood collection for CCI [REDACTED]
- Blood collection for [REDACTED]

**Cycle 2 Day 1**

- Patient-reported QoL assessment
- Complete physical examination
- Vital signs (temperature, blood pressure, pulse rate, respiratory rate, weight, pulse oximetry)
- ECOG PS
- Serum chemistry (unless previous assessment was performed within previous 72 hours)
- Hematology (unless previous assessment was performed within previous 72 hours)
- Urine or serum pregnancy test (female patients of childbearing potential only; must be performed prior to treatment)
- Administer doxorubicin with prophylaxis
- Administer TTI-621 with prophylaxis
- Adverse events
- Concomitant medications and procedures
- Blood collection for CCI [REDACTED]
- Blood collection for [REDACTED]
- Blood collection for [REDACTED]

**Cycle 2 Day 8**

- Brief physical examination
- Vital signs (temperature, blood pressure, pulse rate, and respiratory rate)
- Serum chemistry (unless previous assessment was performed within previous 72 hours)
- Hematology (unless previous assessment was performed within previous 72 hours)
- Administer TTI-621 with prophylaxis
- Adverse events
- Concomitant medications and procedures
- Blood collection for CCI [REDACTED]

**Cycle 3 Day 1**

- Patient-reported QoL assessment
- Complete physical examination
- Vital signs (temperature, blood pressure, pulse rate, respiratory rate, weight, pulse oximetry)

- ECOG PS
- Serum chemistry (unless previous assessment was performed within previous 72 hours)
- Hematology (unless previous assessment was performed within previous 72 hours)
- Urine or serum pregnancy test (female patients of childbearing potential only; must be performed prior to treatment) 12-lead ECG (unless previous assessment was performed within previous 7 days)
- Radiologic assessment of disease status (unless performed within previous 7 days)
- Administer doxorubicin with prophylaxis
- Administer TTI-621 with prophylaxis
- Adverse events
- Concomitant medications and procedures
- Blood collection for CCI [REDACTED]
- Blood collection for [REDACTED]
- Blood collection for [REDACTED]
- Tissue collection for CCI [REDACTED]  
[REDACTED]

***Cycle 3 Day 8***

- Brief physical examination
- Vital signs (temperature, blood pressure, pulse rate, and respiratory rate)
- Serum chemistry (unless previous assessment was performed within previous 72 hours)
- Hematology (unless previous assessment was performed within previous 72 hours)
- Administer TTI-621 with prophylaxis
- Adverse events
- Concomitant medications and procedures
- Blood collection for CCI [REDACTED]
- Blood collection for [REDACTED]

**Cycle 4 Day 1**

- Patient-reported QoL assessment
- Complete physical examination
- Vital signs (temperature, blood pressure, pulse rate, respiratory rate, weight, pulse oximetry)
- ECOG PS
- Serum chemistry (unless previous assessment was performed within previous 72 hours)
- Hematology (unless previous assessment was performed within previous 72 hours)
- 12-lead ECG (unless previous assessment was performed within previous 7 days)
- Urine or serum pregnancy test (female patients of childbearing potential only; must be performed prior to treatment)
- Administer doxorubicin with prophylaxis
- Administer TTI-621 with prophylaxis
- Adverse events
- Concomitant medications and procedures
- Blood collection for CCI [REDACTED]
- Blood collection for [REDACTED]
- Blood collection for [REDACTED]

**Cycle 4 Day 8**

- Brief physical examination
- Vital signs (temperature, blood pressure, pulse rate, respiratory rate)
- Serum chemistry (unless previous assessment was performed within previous 72 hours)
- Hematology (unless previous assessment was performed within previous 72 hours)
- Administer TTI-621 with prophylaxis
- Adverse events
- Concomitant medications and procedures

**Cycle 5 Day 1**

- Patient-reported QoL assessment
- Complete physical examination
- Vital signs (temperature, blood pressure, pulse rate, respiratory rate, weight, pulse oximetry)
- LVEF by transthoracic echocardiogram or MUGA (unless performed within previous 4 weeks)
- ECOG PS
- Serum chemistry (unless previous assessment was performed within previous 72 hours)
- Hematology (unless previous assessment was performed within previous 72 hours)
- Urine or serum pregnancy test (female patients of childbearing potential only; must be performed prior to treatment) Radiologic assessment of disease status (unless performed within previous 7 days)
- Administer doxorubicin with prophylaxis, including cardioprotectant (administration of cardioprotectant must be initiation no later than with Cycle 5, but may be initiated earlier per institutional standard of care)
- Administer TTI-621 with prophylaxis
- Adverse events
- Concomitant medications and procedures
- Blood collection for CCI [REDACTED]
- Blood collection for [REDACTED]
- Blood collection for [REDACTED]

**Cycle 5 Day 8**

- Brief physical examination
- Vital signs (temperature, blood pressure, pulse rate, respiratory rate)
- Serum chemistry (unless previous assessment was performed within previous 72 hours)
- Hematology (unless previous assessment was performed within previous 72 hours)
- Administer TTI-621 with prophylaxis
- Adverse events
- Concomitant medications and procedures

**Cycle 6 Day 1**

- Patient-reported QoL assessment
- Complete physical examination
- Vital signs (temperature, blood pressure, pulse rate, respiratory rate, weight, pulse oximetry)
- ECOG PS
- Serum chemistry (unless previous assessment was performed within previous 72 hours)
- Hematology (unless previous assessment was performed within previous 72 hours)
- 12-lead ECG (unless previous assessment was performed within previous 7 days)
- Urine or serum pregnancy test (female patients of childbearing potential only; must be performed prior to treatment)
- Administer doxorubicin with prophylaxis, including cardioprotectant
- Administer TTI-621 with prophylaxis

- Adverse events
- Concomitant medications and procedures

***Cycle 6 Day 8***

- Brief physical examination
- Vital signs (temperature, blood pressure, pulse rate, and respiratory rate)
- Serum chemistry (unless previous assessment was performed within previous 72 hours)
- Hematology (unless previous assessment was performed within previous 72 hours)
- Administer TTI-621 with prophylaxis
- Adverse events
- Concomitant medications and procedures

***Cycle 7 and Subsequent Cycles, Day 1***

- Patient-reported QoL assessment
- Complete physical examination
- Vital signs (temperature, blood pressure, pulse rate, respiratory rate, weight, pulse oximetry)
- ECOG PS
- Serum chemistry (unless performed within previous 72 hours)
- Hematology (unless performed within previous 72 hours)
- Urine or serum pregnancy test (female patients of childbearing potential only; must be performed prior to treatment)
- Administer TTI-621 with prophylaxis
- Adverse events
- Concomitant medications and procedures

***Cycle 7, Cycle 9, Cycle 11, etc. Day 1***

- Radiologic assessment of disease status (unless performed within previous 7 days)
- Blood collection for **CCI** [REDACTED]
- Blood collection for [REDACTED]
- Blood collection for [REDACTED]

***Cycle 7, Cycle 10, Cycle 13, etc. Day 1***

- 12-lead ECG (unless performed within previous 7 days)

***Cycle 7, Cycle 11, Cycle 15, etc. Day 1***

- Blood collection for **CCI** [REDACTED]

***Cycle 7 and subsequent cycles, Day 15***

- Brief physical examination
- Vital signs (temperature, blood pressure, pulse rate, respiratory rate)
- Serum chemistry (unless performed within previous 72 hours)
- Hematology (unless performed within previous 72 hours)
- Administer TTI-621 with prophylaxis

- Adverse events
- Concomitant medications and procedures

**Cycle 8 Day 1**

- LVEF by transthoracic echocardiogram or MUGA (unless performed within previous 4 weeks)

***Safety Follow-Up Visit (30 + 5 days after last administration of study treatment or before initiation of subsequent anti-cancer therapy, whichever occurs soonest)***

- Patient-reported QoL assessment
- Complete physical examination
- Vital signs (temperature, blood pressure, pulse rate, respiratory rate, weight, pulse oximetry)
- LVEF by transthoracic echocardiogram or MUGA (unless performed within previous 4 weeks with no abnormalities)
- ECOG PS
- Serum chemistry (unless performed within previous 72 hours)
- Hematology (unless performed within previous 72 hours)
- 12-lead ECG
- Urine or serum pregnancy test (female patients of childbearing potential only)
- Radiologic assessment of disease status (unless performed within previous 7 days)
- Adverse events
- Concomitant medications and procedures
- Blood collection for CCI [REDACTED]

***Long-Term Follow-Up***

- Radiologic assessment of disease status (patients who have not experienced disease progression)
- Blood collection for CCI [REDACTED] in participants with an unresolved AE considered by the Investigator as possibly related to or associated with CCI [REDACTED] at the Safety Follow-Up Visit will be asked to return for CCI [REDACTED] blood sampling at approximately 3-month intervals (if feasible given the underlying disease) until the last follow-up of the AE up to a maximum of 12 months.
- Survival (assessed every 12 ± 2 weeks; telephone contact is acceptable)

## 12. STATISTICAL CONSIDERATIONS

### 12.1. Sample Size

#### 12.1.1. Dose Escalation

The number of patients will depend on the number of dose cohorts that will be enrolled before reaching the MTD. It is anticipated that three dose levels of TTI-621 given in combination with a fixed dose of doxorubicin will be evaluated and that at least nine and up to approximately 18 patients will be enrolled to evaluate these three dose levels. On this basis of emerging safety data, additional dose levels may be added. The size and design of the dose escalation phase of the study is consistent with standard 3+3 design with the objective of determining the safety of escalating doses of TTI-621 in combination with fixed dose doxorubicin and establishing TTI-621 doses for further evaluation in the intended patient population.

#### 12.1.2. Expansion Cohorts

Expansion cohorts are planned to evaluate two TTI-621 dose levels in combination with doxorubicin: a low dose of TTI-621 (Cohort A) and a higher dose (Cohort B). A Simon two-stage design will be used for each dose cohort, assuming a baseline overall response rate of 10% with doxorubicin monotherapy. In the Simon two-stage design and an alternative of 25%, a power of 90% and one-sided Type 1 error set at 0.20, each dose level cohort will require 18 patients enrolled and evaluable for response in Stage 1; with at least two clinical responses, an additional 13 patients will be enrolled in Stage 2. The combination will be considered worthy of further study if at least five clinical responses are observed in either 31-patient cohort.

### 12.2. Analysis Populations

The following analysis populations are defined for the study:

**Safety population:** all patients who received at least 1 dose of TTI-621

**Efficacy population:** all patients who received at least 1 dose of TTI-621

**DLT-evaluable population:** all patients who received the full dose of doxorubicin and the planned doses of TTI-621 on Day 1 and Day 8 and have been followed for the entire 21-day DLT period (i.e., Cycle 1) or who have a DLT during Cycle 1 will be considered DLT-evaluable

**Response-evaluation population for Simon two-stage design:** all patients in either Expansion Cohort A (low dose TTI-621) or Expansion Cohort B (high dose TTI-621) who complete at least two cycles of treatment as described in the protocol and have a post-treatment objective disease assessment unless they were withdrawn prior to meeting this criterion for safety or earlier demonstration of objective disease progression

**CCI** [REDACTED]: all patients who received at least one dose of TTI-621 and have at least one evaluable blood sample for analysis collected

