Objective disease assessments will be performed after every second cycle of treatment for 50 weeks and after every third cycle thereafter. A patient enrolled in an expansion cohort who withdraws or is withdrawn from the study prior to the first objective disease assessment for a reason other than disease progression or safety will be replaced in order to meet the statistical criteria for the Simon two-stage design. In the event that the LMS diagnosis is not confirmed during central review for a patient enrolled in the dose expansion portion of the study, the patient must be replaced for purposes of meeting the statistical requirements of the study but may be allowed to continue on treatment after discussion with the Sponsor Medical Monitor. Patients who withdraw from the study without evidence of disease progression will be followed in the Long-Term Follow-Up period for documentation of disease progression or initiation of another treatment as well as survival.

The mechanism of immunotherapy is mechanistically distinct from other types of therapy. The patterns of response and progression to immunotherapeutic agents, such as TTI-621, often differ temporally, qualitatively and quantitatively from those observed with cytotoxic and targeted agents. The goal of immunotherapy is to overcome immunosuppression induced by a tumor and its microenvironment, thereby allowing the immune system to develop or activate an immune response that targets and kills

cancer cells. Some patients have experienced pseudo-progression, in which tumor burden showed an initial surge followed by shrinkage, usually at around weeks, that led to development of immune-related disease response criteria that supports continued treatment beyond progression in patients whose clinical conditions have not worsened and who have not experienced severe toxicities. Recognizing that immunotherapy represents a paradigm shift in oncology treatment, patients with an early observation of disease progression but without deterioration in clinical conditions or unacceptable toxicity and who consent should continue treatment until disease progression is verified by a repeated disease assessment at least four weeks later.

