***Disease Characteristics***

5. Histologically-confirmed high-grade soft tissue sarcoma that is metastatic or locally advanced and not amenable to curative treatment with surgery or radiation
  - In the dose escalation portion of the study, indications will be limited to high-grade leiomyosarcoma, undifferentiated pleomorphic sarcoma, myxofibrosarcoma, dedifferentiated liposarcoma, angiosarcoma and epithelioid sarcoma
  - In the expansion portion of the study, enrollment will be restricted to high-grade leiomyosarcoma that is histologically-confirmed at a central laboratory. The patient may be enrolled based on a current or most recent pathology report that provides sufficient detail to support derivation of the histologic interpretation but a pre-treatment tissue specimen must be made available for confirmation during screening or within the first cycle of treatment
6. Objective evidence of disease progression unless disease is newly-diagnosed
7. Measurable disease per RECIST v1.1 (expansion cohorts); target lesions must not be chosen from a previously-irradiated field unless there has been radiographically and/or pathologically documented tumor progression in that lesion prior to enrollment

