## 6.7 Analysis Populations

### 6.7.1 Full Analysis Set (FAS)

The FAS will include patients who were enrolled, allocated to treatment, and received at least one non-zero dose of study treatment.

This analysis population will be used for baseline summaries and the analysis of efficacy endpoints.

Patients will be classified according to the study treatment actually received. For patients who received a wrong study dose, they would be recoded in protocol deviation and dosing compliance; if the wrong dose occurred only once, the analysis will use the patients' initial planned dose as summary cohorts. If more than one wrong dose occurred, the analysis will use patients' actual dose as summary cohorts. If patients' doses were reduced, safety analysis will use the initial planned dose as summary cohorts. Patients receiving different dosing schedules will be presented in the listings only.

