## 8. Efficacy Analyses

Efficacy analyses will use data from the FAS (for all efficacy endpoints) and will be descriptive in nature. Summary tables and figures will be presented by treatment group as described in Section 6.1, as applicable.

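### The plan does not settle whether expansion patients without central confirmation of leiomyosarcoma count in the Simon decision, and the SAP includes them in the cohort response rate

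*Protocol*

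**What the plan says.** Protocol section 6.2, criterion 5, says of the expansion portion that "enrollment will be restricted to high-grade leiomyosarcoma that is histologically-confirmed at a central laboratory". The same criterion lets a patient enroll on a local pathology report, provided tissue reaches the central laboratory during screening or the first cycle. Treatment can therefore begin before the central result is known.

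If central review does not confirm the diagnosis, section 5.1 says "the patient must be replaced for purposes of meeting the statistical requirements of the study but may be allowed to continue on treatment"; the medical monitor has to be consulted first. The synopsis and section 12.3.3 say the same.

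Section 12.2 defines the response-evaluation population for the Simon design as all Cohort A or B patients "who complete at least two cycles of treatment as described in the protocol and have a post-treatment objective disease assessment", except that patients withdrawn earlier for safety or progression are kept. Histology is not mentioned.

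The SAP takes a different route:

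- Section 6.7.1: "The FAS will include patients who were enrolled, allocated to treatment, and received at least one non-zero dose of study treatment".
- Section 8: "Efficacy analyses will use data from the FAS (for all efficacy endpoints) and will be descriptive in nature".
- Section 8.2 keeps all patients of the full analysis set (FAS) in the response-rate denominator.
- Section 6.7 defines the FAS, the safety set and the DLT-evaluable set. It has no response-evaluable set and no confirmed-histology set.
- Section 4.3.2 repeats the Simon rule. It reports that Cohort B enrollment ended after its 18 Stage 1 patients and that the Simon design does not apply to Cohort C.

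**The concern.** There are two separate problems.

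**The Simon count.** Replacing a patient to meet the statistical requirements implies that the patient does not hold one of the 18 or 31 places. Section 12.2, read literally, keeps that patient in once two cycles and a scan are done. Section 12.3.3 sharpens the conflict. For early withdrawals it states that they are replaced and are left out of the response-evaluable population. Its next sentence, on unconfirmed histology, states the replacement but not the exclusion.

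**The reported response rate.** The expansion portion is meant to measure activity in high-grade leiomyosarcoma. Following the SAP as written gives a primary response rate, and PFS and OS, that include patients whose leiomyosarcoma was not confirmed. No confirmed-only result is planned beside them.

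At stake are a further-study decision that could turn on which section is read, and a headline estimate that does not match the population in the objective.

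**Working it through.** **Inputs.** Protocol section 12.1.2 gives the design: "assuming a baseline overall response rate of 10% with doxorubicin monotherapy", an alternative of 25%, and "a power of 90% and one-sided Type 1 error set at 0.20". Stage 1 has 18 patients and continues at 2 or more responses. Stage 2 adds 13, and success is 5 or more of 31.

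**The plan's own figure.** With response rate p, the probability of success is

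Σ over x ≥ 2 of P(Bin(18, p) = x) × P(Bin(13, p) ≥ 5 − x).

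At p = 0.10:

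| Stage 1 responses | Probability | P(Stage 2 reaches a total of 5) | Product |
|---|---|---|---|
| 2 | 0.2835 | 0.1339 | 0.0380 |
| 3 | 0.1680 | 0.3787 | 0.0636 |
| 4 | 0.0700 | 0.7458 | 0.0522 |
| 5 or more | 0.0282 | 1 | 0.0282 |

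The sum is 0.182, within the 0.20 limit. The same formula at p = 0.25 gives power 0.902. The design reproduces. These are also its properties if unconfirmed patients are replaced and left out of the counts.

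**Conditional sensitivity.** Suppose instead that k replaced patients are counted on top of 18 + 13 confirmed ones, with cut-offs 2 and 5 unchanged. Their responses, Bin(k, q), are added to the stage in which they fall. With the confirmed rate at 10%:

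| Extra patients counted | q = 10% | q = 9% to 27% |
|---|---|---|
| 1, in Stage 2 | 0.197 | 0.195 to 0.222 |
| 1, in Stage 1 | 0.201 | 0.199 to 0.233 |
| 3 (2 in Stage 1, 1 in Stage 2) | 0.237 | 0.231 to 0.337 |

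The 9% to 27% range is the doxorubicin response range for soft tissue sarcoma quoted in protocol section 3.4 and SAP section 1.1. Applying it to unconfirmed patients is an assumption. So is k, which the documents do not give.

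**The 2-of-18 cut-off alone**, at 10% throughout: the chance of 2 or more responses is 0.550 with 18 patients, 0.580 with one extra counted and 0.635 with three.

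**One patient near the boundary.** Suppose 4 of 31 confirmed patients respond: 12.9% (Wilson 95% CI 5.1 to 28.9), which fails the rule. Adding one unconfirmed responder gives 5 of 32: 15.6% (6.9 to 31.8). The SAP would report the second figure. Whether it also passes the rule is what the documents leave open.

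**Which cohorts.** By SAP section 4.3.2, only Cohort A can reach 5 of 31. Cohort B is affected only at 2 of 18, and Cohort C has no Simon cut-off. The inclusion of unconfirmed patients in response rate, PFS and OS applies to all three.

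**The case against.** A reader might infer that the replaced patient and the replacement both count toward the five responses. The documents do not support that as a rule. No section says it, and the replacement clause points the other way: for the expansion cohorts, the statistical requirements can hardly mean anything but the Simon design. The cut-off is also tied to a 31-patient cohort, and no rule is given for 32 or more. This objection stands, so every figure above 0.182 is conditional. With one extra patient at 10%, the change around the 0.20 limit is negligible.

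Nor should unconfirmed be read as another sarcoma. The documents do not say what non-confirmation covers.

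It can also be said that an all-treated response rate is legitimate, follows protocol section 12.3.3 and is labelled descriptive. That is fair, and it is a reason to keep it. It does not explain why no confirmed-histology rate accompanies it.

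Finally, there are safeguards. SAP section 7.1 lists histology, SAP section 7.3 lists eligibility failures and tabulates major deviations, and protocol section 12.4 has deviations that could affect efficacy identified before database lock. The patients can therefore be found, but no analysis set acts on what is found.

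**Conclusion.** The point holds in two parts of different strength.

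- **Certain from the text:** under SAP sections 6.7.1, 8 and 8.2, patients without central confirmation enter the cohort response rate in Cohorts A, B and C, and PFS and OS follow the same set. No confirmed-histology or response-evaluable set exists in the SAP.
- **Unresolved in the text:** protocol sections 5.1 and 12.3.3 conflict with 12.2 on whether replaced patients' responses count toward the Simon cut-offs. The documents establish a conflict, not an inflated error rate.

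If such patients were counted, type I error would go from 0.182 to about 0.20 with one and 0.237 with three at a 10% response rate (0.231 to 0.337 over 9% to 27%). This rests on unchanged cut-offs, an assumed number unconfirmed and assumed response rates. The 5-of-31 consequence is confined to Cohort A. The matter should be corrected, but it does not undermine the design, which performs as stated when the counts are restricted to confirmed patients.

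**What to change.** State in the SAP that patients without central confirmation of high-grade leiomyosarcoma are excluded from the Simon response-evaluation population and from the 2-of-18 and 5-of-31 counts. Align protocol section 12.2 at the next amendment.

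In SAP section 6.7, define a centrally confirmed subset of the FAS for the expansion cohorts. Report its response rate with a Wilson 95% interval beside the all-treated rate.

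SAP section 1.2 allows the efficacy plan to change before database lock, and the central review that supplies the flag is already required. The cost is SAP wording, one derived flag, one more table row and a slightly smaller denominator for the confirmed rate. The protocol wording needs IRB approval under section 14.9, which is why it can wait for an amendment made for other reasons. No treatment or visit changes.
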